- Eligibility Source documents: Initial consult note, pre-implant sleep study, pre-implant DISE report, HGNS titration report, HGNS efficacy sleep study report (if applicable), current medications list (reconciled), all Inspire® therapy reports leading up to enrollment.

4C. Study Timeline - Pages 5 to 10

- Enrollment (Study Day 1): HGNS therapy will be deactivated (set to 0.0 V) for one week. Sham threshold determination may be done during this visit, or during randomization visit (see below study week 2). RSC will schedule cardiovascular and sympathetic testing, if possible. The patient will also be instructed about neurobehavioral testing and will perform a practice administration of the DSST and PVT. Form 1 will be completed by RSC (remote #, current therapy status, non-dominant arm diameter, WatchPAT digit determination, medication reconciliation, sham threshold determination (volts), and active therapy setting (volts)). If needed, the patient will contact RSC after the appointment to provide the remote number. The patient will also be given an "on-study card" containing contact information for the research coordinator. The patient will be told to contact the coordinator if any health care providers intend to make changes to the patient's blood pressure medication. An enrollment questionnaire will be completed by the patient:
 - o Do you take any medications or substances to improve daytime alertness?
 - Do you take any medications or substances to improve sleep quality?
 - o How many hours do you sleep each night, on average?
 - ESS, ISI, FOSQ, Snoring VAS
- Washout Period 1 (Study Week 1): The patient will not use HGNS for 1 week
- Randomization Visit (Study Week 2 with [name] and RSC):
 - a. Patient will fill out "washout questionnaire":
 - Patient attestation statement about therapy non-use
 - Have you taken any substance to increase daytime alertness (e.g. caffeine)?
 - Have you taken any substance to improve sleep quality (e.g. alcohol)?
 - o Have you had any episodes of falling asleep while driving?

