- Sympathetic Measurements (Study Week 6, Day 2): The patient will be laid supine in a comfortable position prior to testing. The 15-minute protocol will involve pre-ejection period (PEP) testing by impedance cardiography.

Prior to the testing, subjects will have been informed of the pre-visit protocol: no food >6 hours before testing; withhold all cardiac and blood pressure medications on the day of testing; no caffeine or alcohol >12 hours before testing; avoid exercise on morning of testing; refrain from cigarette smoke exposure >12 hours before testing; and abstain from vitamin supplementation >72 hours before testing.

Pre-ejection Period (PEP): Each patient will be fitted with the Biopac NICO100C Impedance Cardiography (ICG) Noninvasive Cardiac Output Module (Biopac, Goleta CA USA). This device will record the ECG and the ICG continuously during a 10-minute period through eight, disposable, pre-gelled Ag/AgCl electrodes. PEP will be calculated as the average interval (milliseconds) from the onset of left ventricular depolarization, reflected by the Q-wave onset in the ECG to the opening of the aortic valve, reflected by the B-point in the ICG signal.

- o At the end of this visit, the patient will be set to 0.0V for washout period 2.
- Procedure Day Questionnaire: Therapy attestation statement, medication reconciliation, caffeinated beverages per day, sleep-promoting substance use (e.g. alcohol), ESS, FOSQ, ISI, Snoring VAS.
- Neurobehavioral Measurements (Study Week 6, Day 2): The patient will perform neurobehavioral tests on a designated laptop in a quiet room at the Otorhinolaryngology clinic. Each subject will perform a unique version of the digital symbol substitution test

and psychomotor vigilance test. The laptop is calibrated for timing precision. All patients will be monitored by a trained study staff member to ensure adherence to test procedure protocol.

Prior to testing, subjects will have been informed of pre-visit protocol: abstain from testing if sick; abstain from testing if <1 hour of waking up; and abstain from testing if >16 hours of being awake.

- Washout Period 2 (Study Week 6-7): The patient will not use HGNS for 7 days.

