- Crossover Visit & Therapy (Study Week 7): The patient will be switched to the other intervention arm (treatment to sham vs. sham to treatment) for 28 days, or for the duration spent on the previous intervention arm. The research coordinator will program the device at the specified amplitude level, per Form 1.

Patient will fill out "washout questionnaire #2":

- Patient attestation statement about therapy non-use.
- Have you taken any substance to increase daytime alertness (e.g. caffeine)?
- Have you taken any substance to improve sleep quality (e.g. alcohol)?
- o Have you had any episodes of falling asleep while driving?

The research coordinator will reprogram the patient's HGNS to the amplitude the patient was using prior to study participation. The research coordinator will instruct the patient to use therapy the same night.

• Blinding Adequacy Phone Call (Week 7, Day 2)

Phone call: second morning questionnaire:

- 1. Do you think you are on "low" or "regular" treatment?
- 2. Why you do think so?
 - a. Increased snoring per bed partner
 - b. Increased fatigue
 - c. Morning headache
 - d. Nighttime awakening

e.	Other					

Weekly Check-In Phone Call (Week 8, Week 9, Week 10)

RSC weekly call with patient re: usage. Goal is to encourage use (>20h/week). Document any changes in blood pressure medication.

Document any AEs, issues or concerns.

• 24-hour Ambulatory Blood Pressure & WatchPAT (Study Week 9, Night 1):

The patient will be programmed and mailed 24-hour ambulatory blood pressure testing (ABP) and WatchPAT, scheduled to arrive between 2-7 days before physiology testing.

RSC will ensure that ABP, WatchPAT and Inspire® times are synchronized. For convenience and/or patient preference, the patient may meet with RSC in person to pick up the equipment.

- Sympathetic, Vascular, & Neurobehavioral Measurements & Wrap-Up (Study Week 10, Day 2):
 - 1. RSC will download therapy compliance data from the patient's remote.
 - 2. The patient will undergo the same set of testing as above.
 - 3. If any of the ABP or WatchPAT data is invalid or incomplete, the patient may be asked to repeat these tests, at the discretion of the PI. In this case, the patient will remain at the current setting and will need to return to have their HGNS reset to the pre-study amplitude.
 - 4. Procedure Day Questionnaire: Therapy attestation statement, medication reconciliation, caffeinated beverages per day, sleep-promoting substance use, ESS, FOSQ, ISI, Snoring VAS.

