Potential study risks: Patients will undergo laboratory testing of their cardiovascular system following each intervention arm. They will undergo pre-ejection period, by which an external chest monitor and electrocardiogram are used to calculate the time between electrical and mechanical motion of the heart. While muscle sympathetic nerve activity represents an invasive procedure, microneurography is a safe, well-tolerated, standard human research procedure that has been used in multiple studies with a range of patient diagnoses – greater than 200 procedures performed at Emory University by [name], collaborating investigator, without complication. Approximately 7% of subjects have discomfort, including tingling, soreness at the electrode insertion site, or muscle weakness in the leg 1 to 2 days following the procedure; this usually resolves within a week. There are no known long-term risks. Participants are free to discontinue microneurography at any time for any reason.

As part of the experimental study design, the subject will be assigned to a 4-week sham intervention period during which they will most likely experience a recurrence of symptoms of OSA that may have been alleviated by the HGNS during clinical care. As only patients who

had previously untreated OSA therapy are eligible for the study, these patients will experience a return to pre-operative symptoms. We have deliberately excluded patients who were actively using CPAP or other OSA therapy prior to HGNS surgery, as placing these subjects through a period of inadequate treatment (sham period) bears ethical concern. Subjects will be advised to avoid or exercise increased caution when driving or operating heavy machinery during the sham therapy period when they are more likely to feel sleepy. Additionally, patients will wear a blood flow measurement device for 24 hours, which is also well tolerated and does not disturb sleep or other daily activities. Wearing the WatchPAT device while sleeping may result in decreased sleep quality during the night of the testing. However, sleep quality typically returns to usual the following night, with no lasting effects noted.

Potential study benefits: This study is not designed to benefit subjects directly. However, the study results may help doctors to better understand sleep apnea and might be used to help people with sleep apnea in the future.

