Risk/Benefit Ratio: As there are few risks in measuring cardiovascular data apart from recurrence of OSA symptoms during the 4-week sham period and there are the possible benefits of better understanding sleep apnea and how to treat people with sleep apnea in the future, the risks of participating in this study are outweighed by the potential benefits.

8. Device Management

Penn owns WatchPAT and ambulatory blood pressure devices, which will be managed, dispensed, and received back from subjects by the study team. Recordings will be handled and scored in accordance with best clinical practices.

9. Feasibility

Sample Size Feasibility: We have recruited 17 subjects (16 have successfully completed the study) since January, 2018, and plan to complete recruitment in 2020.

Technical Feasibility: With regard to Aim 1, 16 subjects successfully completed both sets of 24-hour ambulatory blood pressure testing.

Project execution feasibility: PI has 50% protected research time through 2021. PI will devote 20% of his efforts to ensure the successful completion of this project.

10. Potential Pitfalls, Solutions, and Contingency Plans

1. Study Design

a) The study sample reflects a selective subset of patients with moderate-severe OSA, limiting the generalizability of these findings. Among others, the inclusion criteria are 1) unable to consistently use PAP, and 2) body-mass index < 32 kg/m². In clinical practice, this represents only 20% of the moderate-severe OSA population as BMI > 32 kg/m² is an exclusion criterion for HGNS and roughly 50% of patients can comply with PAP. From a population health perspective, however, this selected group represents a not insignificant 2% of the U.S. adult population. ⁴ Note: since this research protocol was created, BMI was

removed as an exclusion criteria for HGNS.

- b) We are performing measurements at 2 time points only, immediately after sham and treatment interventions. While we do not capture baseline values, these measures will allow us to compare the individual effects of sham and active therapy. We predict that a 2-week washout period, in contrast to the 1-week withdrawal period in the STAR trial, ²³ will provide a return to baseline for ABP at 2 weeks. ³¹

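### Section 7 weighs only the 4-week sham as time with recurrent OSA and limits its driving caution to it; two 7-day device-off washouts are left out of both

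*Combined protocol and SAP*

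**What the plan says.** Under Potential study risks, section 7 describes a "4-week sham intervention period during which they will most likely experience a recurrence of symptoms of OSA". The Risk/Benefit Ratio paragraph calls the risks of the cardiovascular measurements few "apart from recurrence of OSA symptoms during the 4-week sham period" and concludes that the potential benefits outweigh them. The only driving instruction in the document is also in section 7: subjects are to be told to "avoid or exercise increased caution when driving or operating heavy machinery during the sham therapy period when they are more likely to feel sleepy". Section 7 mentions neither washout.

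The schedule in section 4C has three stretches without therapeutic stimulation:

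- **Washout 1.** At enrollment, "HGNS therapy will be deactivated (set to 0.0 V) for one week".
- **Washout 2.** At the end of the first test visit "the patient will be set to 0.0V for washout period 2", and "The patient will not use HGNS for 7 days".
- **Sham.** One of the two intervention periods. The second period is set "for 28 days, or for the duration spent on the previous intervention arm".

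Elsewhere the protocol treats the washouts as carrying risk. The section 2 footnote requires a pregnancy test before each washout where applicable, because treatment is being stopped. Both washout questionnaires in section 4C ask whether the patient has fallen asleep at the wheel.

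**The concern.** A risk/benefit statement should rest on the exposure that the schedule produces. Here the only recurrence weighed is the sham period, although every patient, whatever the sequence, also spends two scheduled weeks with the device off.

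The caution has the same gap. Its stated reason is sleepiness. Sham leaves some stimulation on, at a level that moves the tongue without obvious protrusion (section 4C, Sham Threshold Determination), whereas the washouts leave none. On the protocol's own reasoning, nothing supports advising care during sham and not at 0.0 V. Drowsy driving is a serious hazard and endangers other people as well as the patient.

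A smaller point of clarity is that patients are blinded to the order of sham and treatment, so they cannot know when a caution tied to the sham period applies. The reference to sleepiness gives them only a partial cue.

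**Working it through.** **Inputs** (all from the combined protocol and SAP)

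- Washout 1: 7 days (section 4C, Enrollment and Washout Period 1)
- Washout 2: 7 days (section 4C, Washout Period 2)
- Sham: 28 days (section 4C, Crossover Visit & Therapy)
- Recurrence counted in section 7: 4 weeks

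**The plan's own figure.** 28 / 7 = 4.0 weeks. Section 7 is right about the length of the sham period. The same arithmetic shows that its sham period cannot be read as including the washouts.

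**Total without effective therapy, by the stated durations**

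- 7 + 28 + 7 = 42 days = 6.0 weeks
- Share counted in section 7: 28 / 42 = 67%
- Excess over the counted figure: 14 / 28 = 50%
- Share outside the driving caution: (7 + 7) / 42 = 33%

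**By sequence, same durations**

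| Sequence | Time without effective therapy |
|---|---|
| Sham first | 7 + 28 + 7 = 42 consecutive days |
| Treatment first | 7 days, then later 7 + 28 = 35 consecutive days |

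**By the visit-week labels, treatment first.** Section 4C dates the first test visit Week 6, Day 2, lists "Crossover Visit & Therapy (Study Week 7"), and dates wrap-up Week 10, Day 2. Counting Week w, Day d as study day 7(w − 1) + d:

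- First test visit: 7 × 5 + 2 = day 37
- End of a 7-day washout 2: 37 + 7 = day 44 (Week 7, Day 2)
- Wrap-up: 7 × 9 + 2 = day 65
- Sham: 65 − 44 = 21 days
- Consecutive block: 7 + 21 = 28 days
- Total with washout 1: 7 + 28 = 35 days
- Share outside the caution: 14 / 35 = 40%

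The 28-day block does not depend on the exact crossover day, because 65 − 37 = 28 wherever in Week 7 crossover falls.

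**Other wordings in the document.** The hypotheses in section 3 speak of a 30-day sham, which gives 7 + 30 + 7 = 44 days. Section 10, item 1b, refers to a 2-week washout; if each washout lasted that long, the total would be 14 + 28 + 14 = 56 days, or 8 weeks. The note to Figure 3 allows ±14 days at each step. The figure is not in the available text, so how the allowance accumulates is unknown and no bound is given here.

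**Is a driving instruction for the washouts given anywhere else?**

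- The exclusion in section 2 concerns drowsy-driving accidents or near misses in the year before implantation.
- The driving question in each washout questionnaire is asked after that week has passed.
- The weekly calls fall in Weeks 3–5 and 8–10, outside the scheduled washouts.
- Section 10, item 1d, says patients are educated before enrollment about returning symptoms, without mentioning driving.

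None of these is a prospective driving instruction for the device-off weeks.

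**The case against.** The strongest objection is that section 7 only describes advice to be given and is not itself the warning to patients. The consent form, which would probably carry that warning, was not available and may be wider. Blinding also pushes in practice towards general advice at enrollment, which is the day the device is first switched off. This stands to the extent that nothing here shows patients go unwarned. It does not repair section 7, whose wording, followed literally, leaves out two untreated weeks.

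A second objection is that 4 weeks is correct for the sham and was never offered as a total, and that a reader of section 4C has every component. The first part is true of the Potential study risks paragraph. It fails for the Risk/Benefit Ratio paragraph, which makes sham-period recurrence the sole exception to the claim of few risks, so the 4 weeks become the whole recurrence exposure weighed.

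Third, days without therapy are not shown to be days with symptoms; the document gives no time course for sleepiness returning within a 7-day washout. This stands: 42 days measures time without effective therapy, not observed recurrence. The protocol nevertheless plans for drowsy driving in those weeks by asking about it after each one.

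Finally, safeguards exist. Recent drowsy-driving events are excluded, patients are taught that symptoms may return, and the washouts are open, so patients know the device is off. These lower the seriousness without supplying the missing instruction.

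**Conclusion.** The concern holds. Section 7 discloses the kind of risk but understates its scheduled duration: 28 days counted against a nominal 42. The driving caution leaves out 14 days in both sequences, which is 33% of the nominal total, or 40% of the 35 days that the week labels imply for a treatment-first patient.

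The totals assume 7-day washouts, one sham period of the stated length and no scheduling slippage. The omission of the washouts does not depend on which sham length applies. Whether 6 weeks would alter the risk/benefit conclusion is not shown. The finding is limited to the protocol text and does not affect the validity of the trial's results. It should be fixed because the hazard is serious, every patient is scheduled for both washouts, and the remedy is cheap.

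**What to change.** In both the Potential study risks and Risk/Benefit Ratio paragraphs of section 7, state about 6 weeks without effective therapy: a 1-week washout, a 4-week sham and a second 1-week washout. Say that these may run consecutively and may be shorter or longer with scheduling.

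Replace the caution with one instruction that does not depend on allocation and is given to everyone at enrollment. For example: *From the day the device is first switched off until pre-study therapy is restored at wrap-up, including both washouts and both blinded periods, avoid driving and using heavy machinery or take extra care when doing so.* Adding only the washouts to the present sentence would close the duration gap but leave the blinding ambiguity.

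Then check that the patient information says the same.

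The cost is a wording amendment to section 7 and, if needed, to the patient information. The stated risk becomes less favourable, and patients take extra care during one 28-day period in which they are in fact treated. Design, randomization and analysis are unchanged.

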Hypothesis: The pulse wave velocity parameters will be improved at therapeutic levels of hypoglossal nerve stimulation and returned to pre-operative levels after 30-day sham period

Change in Digit Symbol Substitution Test (DSST) score

Aim 5: Determine the impact of hypoglossal nerve stimulation on digital symbol substitution test score in this cohort of patients with moderate-severe obstructive sleep apnea

Hypothesis: The digital symbol substitution test score will be improved at therapeutic levels of hypoglossal nerve stimulation compared to after 30-day sham period

Change in Psychomotor Vigilance Test (PVT) score

[figure not shown]
Aim 6: Determine the impact of hypoglossal nerve stimulation on psychomotor vigilance test score in this cohort of patients with moderate-severe obstructive sleep apnea

Hypothesis: The psychomotor vigilance test score will be improved at therapeutic levels of hypoglossal nerve stimulation compared to after 30-day sham period

4. Procedures and Data Collection

4A. *Pre-Study Procedures:* All patients in the cohort will have undergone implantation of HGNS for OSA at the University of Pennsylvania or Thomas Jefferson University as part of their ongoing care for their OSA. HGNS therapy is not experimental and is not under investigation per se for efficacy in this study. **Figure 3** shows the study flow. Patients will receive compensation for travel and time spent in the study (\$100 per visit, plus \$10 parking reimbursement for each cardiovascular measurement visit; total=up to \$520). Reimbursement for parking may also be available. Compensation will be pro-rated, and will be in the form of mailed checks and/or ClinCards.

Figure 3: Study Flow

Note: We will leave +/- 14 days at each step to accommodate for scheduling issues, etc.

- 1. HGNS Device Implantation: Under general anesthesia, the HGNS device is implanted via 3 incisions: right neck (stimulation lead), right upper chest (pulse generator) and right lower chest (respiratory sensor). The incisions are connected via a tunneling device, integrating the system components. The pulse generator, using technology from cardiac pacemakers, utilizes the signal from the pressure sensor for timing of stimulation to the tongue nerve. Patients are monitored in post-anesthesia recovery until stable for discharge. The device remains "off" for 1 month to allow for adequate healing.

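### The primary paired t-test has no period term although treatment order is randomised; the washout rationale and the period 2 visit labels also need correcting (minor)

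*Combined protocol and SAP*

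**What the plan says.** **Order and analysis.** Section 4C (Randomization technique) allocates patients to sham first or treatment first in blocks of 10, with 100 slots. Section 6, Aim 1, compares sham and active 24-hour systolic pressure by a paired t-test. Neither that test nor the accompanying regression includes period or sequence. Section 6 sizes the trial at 60 for a 4 mmHg difference with SD 11. Section 10 (1. Study Design, d) allows for 10–15% dropout.

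**Washout.** Section 10 (1. Study Design, b) argues: "We predict that a 2-week washout period, in contrast to the 1-week withdrawal period in the STAR trial", will bring ambulatory pressure back to baseline. The schedule in Section 4C says of washout 1, "The patient will not use HGNS for 1 week", and of washout 2, "The patient will not use HGNS for 7 days". The note to Figure 3 adds: "We will leave +/- 14 days at each step to accommodate for scheduling issues, etc".

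**Period 2 calendar.** After a Week 7 crossover, the second setting runs "for 28 days, or for the duration spent on the previous intervention arm". The pressure recording is headed "24-hour Ambulatory Blood Pressure & WatchPAT (Study Week 9, Night 1", its equipment is "scheduled to arrive between 2-7 days before physiology testing", and the final visit is headed "Sympathetic, Vascular, & Neurobehavioral Measurements & Wrap-Up (Study Week 10, Day 2". Check-in calls are listed for Weeks 8, 9 and 10.

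**The concern.** In a two-period crossover, anything that moves blood pressure between the first and second period adds to the active-minus-sham difference in one sequence and subtracts from it in the other. A bare paired t-test treats that systematic split as noise, so power falls. If the sequences finish with different numbers of completers, the split no longer cancels and part of it enters the estimate. The plan already concedes limited power (Section 10, 2. Study Results, b), so an avoidable loss on the primary endpoint deserves attention.

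The washout sentence matters for a different reason. The plan records no baseline ambulatory pressure, so return to baseline cannot be checked from the trial's own data and rests on the written argument. That argument describes a washout twice as long as the scheduled one, and claims an advantage over a comparator trial whose withdrawal was also one week.

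**Working it through.** **1. Reproduce the plan's figures.** Inputs from Section 6: difference 4 mmHg, SD 11, two-sided alpha 0.05, power 0.80.
- n = ((1.96 + 0.842) × 11 / 4)² = 59.4, so 60, as stated.
- Power for 3 mmHg at n=60: 3 / (11/√60) = 2.11, and Φ(2.11 − 1.96) = 0.56, as stated in Section 10.

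The plan therefore uses 11 as the SD of the within-patient difference, and so does this check. With the t distribution, power for 4 mmHg at n=60 is 0.791 on 59 degrees of freedom, and also 0.791 on the 58 left after adding a period term.

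**2. How a period effect enters.** Let δ be the true active-minus-sham effect and π the shift from period 1 to period 2. The mean difference is δ + π in sham-first patients (number n₁) and δ − π in treatment-first patients (n₂).
- Bare paired mean: δ + π(n₁ − n₂)/(n₁ + n₂).
- Average of the two sequence means: δ, whatever n₁ and n₂ are.
- Balanced case: the variance estimated by the bare test rises from 121 to about 121 + π². For π = 3 the SD is √130 = 11.4.

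**3. Balanced sequences, 30 and 30.** The documents give no period effect, so the values of π are assumptions. Power for 4 mmHg, from simulation of 400,000 trials per setting:

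| Period effect (mmHg) | Bare paired t-test | With period term |
|---|---|---|
| 0 | 0.79 | 0.79 |
| 1 | 0.79 | 0.79 |
| 3 | 0.77 | 0.79 |
| 5 | 0.73 | 0.79 |

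**4. Unequal completers.** Assume 60 enrolled and 15% dropout, leaving 51.
- Dropout at random: one SD of the imbalance is √(60 × 0.15 × 0.85)/51 = 0.054. Times 1 to 3 mmHg, this is 0.05 to 0.16 mmHg. It averages zero over repeated trials; this is the typical shift in a single one.
- All dropout in one sequence (30 v 21): 9/51 = 0.18. Times 1 to 3 mmHg, this is 0.18 to 0.53 mmHg. In simulation with π = 3, the bare estimate of a true 4 mmHg averages 4.53 or 3.47 by direction; the period model averages 4.00.
- Cost of the term at 30 v 21 with no period effect: SE (11/2)√(1/30 + 1/21) = 1.56, against 11/√51 = 1.54; power 0.71 against 0.72.

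**5. Washout and calendar.** Each washout is 7 days. In either sequence the sham recording nominally follows 7 + 28 = 35 days without therapeutic stimulation, which is 35/14 = 2.5 times the two weeks in the rationale.

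In period 1, randomisation is in Week 2, calls are in Weeks 3–5 and testing is in Week 6. In period 2, crossover is in Week 7 and calls are in Weeks 8–10, and Week 7 plus 28 days is Week 11. The printed labels are Week 9 for the recording and Week 10 for testing. Week 9, Night 1 is about 8 days before Week 10, Day 2, outside the 2–7 day delivery rule. Three features of the plan therefore speak against the Week 9 label.

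**The case against.** Randomising order in blocks of 10 already makes a period effect largely cancel, so the paired t-test is a defensible analysis. With balanced sequences a period effect makes it conservative: simulated type I error is 0.047 at 2 mmHg and 0.039 at 4 mmHg, so false positives do not rise. No period effect is documented. Section 10 links dropout to symptoms returning on sham, and both sequences include a sham period, so nothing suggests one-sided loss. The plan also does not say whether 60 means enrolled or completing patients. All of this stands and keeps the point minor. It does not justify omitting a term that costs almost nothing.

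Two stronger readings of the washout text are tempting. A reader might infer that a one-week washout lets the active effect carry over into the primary comparison. The documents do not support that: pressure is recorded at the end of each setting, nominally 35 days after therapeutic stimulation stops. Even a sham period cut by the full 14-day allowance leaves 7 + 14 = 21 days. Section 10 predicts return at two weeks; it does not say that a shorter time fails.

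A reader might also take the Week 9 label literally. Treatment-first patients would then have 7 + 13 = 20 days before the sham recording, against 35 for sham-first patients, and shortening by 7 days or more would put them below two weeks (20 − 7 = 13). But that label conflicts with the 28-day or matched-duration rule, the delivery rule and the call schedule. It is most likely a slip.

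The washout sentence cannot be rescued by adding the two washouts, because a treatment period separates them. Nor can the scheduling allowance rescue it, because that can shorten a washout as well as lengthen it.

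**Conclusion.** The point holds, at minor severity. The main issue is that the primary analysis leaves out period in a trial that randomises order. With balanced sequences the estimate is unbiased, and the loss is 0 to 2 points of power for an assumed period effect of 1 to 3 mmHg, and about 6 points at 5 mmHg. With unequal completers the typical shift is 0.05 to 0.16 mmHg, or 1 to 4% of the 4 mmHg target. The 0.18 to 0.53 mmHg range should not be read as expected bias: it needs 15% dropout, all from one sequence, which nothing in the documents suggests. These sizes rest on an SD of differences of 11, as the plan's own calculation implies, and on assumed period effects; the unequal-completer figures also assume 60 enrolled.

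The washout length and the period 2 labels are errors of text. On the nominal schedule they have little consequence for the primary result.

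**What to change.** 1. **Section 6, Aim 1.** Analyse 24-hour systolic pressure with treatment and period terms: the average of the two sequence means of active minus sham, with its 95% confidence interval, using the pooled within-sequence variance on n − 2 degrees of freedom. Report completers per sequence.
2. **Section 10, 1. Study Design, b.** State a one-week washout, drop the contrast with the comparator trial, and rest return to baseline on washout plus time on sham, nominally 35 days.
3. **Section 4C, period 2.** Move the pressure recording and the testing visit to the end of the 28 days, about Week 11, mirroring period 1.

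The cost is one degree of freedom and text edits; n=60 is unchanged. Power is 0.791 with or without the term when sequences are balanced and there is no period effect. If 60 are enrolled, completers end at 30 v 21 and there is no period effect, the term costs about 0.01 power (0.71 against 0.72).
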